## 8.1 Screening

### Screening

All participants must provide signed ICFs prior to performing any study specific procedures. Participants will be evaluated against all study inclusion and exclusion criteria.

After signing the study ICFs, screening assessments should be completed within 28 days prior to enrollment ([Table 8-1](#)). A patient who has a laboratory tests result(s) that does not satisfy the entrance criteria may have the test(s) repeated. These test(s) may be repeated as soon as the investigator believes the re- test result(s) is/are likely to be within the acceptable range to satisfy the entrance criteria, but may be completed within approximately 3 weeks of the original screening visit date. In this case, the Participant will not be required to sign another ICF, and the original participant ID number assigned by the investigator will be used. In the event that the laboratory test(s) cannot be performed within 3 weeks of the original screening visit, or the re-test(s) do not meet the entrance criteria, or other eligibility criteria have changed and are not met anymore, the patient is considered a screen failure, and must be discontinued from the study.

A new ICF will need to be signed if the investigator chooses to re-screen the patient after a patient has screen failed, and the Participant ID number will change. All required screening activities must be performed when the patient is re-screened for participation in the study. An individual patient may only be re-screened once for the study. Once the number of patients screened and enrolled is likely to ensure target enrollment, the Sponsor may close the study to further screening. In this case, the patients who screen failed will not be permitted to re-screen. Bone marrow and peripheral blood pathology specimens (i.e. bone marrow slides, bone marrow biopsy block if applicable, peripheral blood samples) prepared locally for establishing the MDS diagnosis at the time of screening, should be sent to the Novartis designated central laboratory for storage. A copy of the corresponding pathology reports should be collected and sent to the Novartis designated central laboratory for storage. Central morphology review of the pathology specimens may be performed, if deemed necessary.

#### 8.1.1 Eligibility screening

Participant eligibility will be checked once all screening procedures are completed.

#### 8.1.2 Information to be collected on screening failures

Participants who sign an informed consent form and subsequently found to be ineligible prior to enrollment will be considered a screen failure. The reason for screen failure should be recorded on the appropriate Case Report Form. The demographic information, informed consent, and Inclusion/Exclusion pages must also be completed for screen failure participants. No other data will be entered into the clinical database for participants who are screen failures, unless the participant experienced a serious adverse event during the screening Phase (see SAE section for reporting details, [Section 10.1.3](#)).

## 8.2 Participant demographics/other baseline characteristics

Demographics and other baseline characteristics data to be collected on all participants include:

- Demography including date of birth, sex, predominant race and ethnicity (where permitted).
- Height and weight (see [Table 8-1](#)).
- Medical history (e.g., important medical, surgical, and allergic conditions from the patient's medical history which could have an impact on the patient's evaluation) / current medical conditions (e.g., all relevant current medical conditions which are present at the time of signing informed consent). Ongoing medical conditions, symptoms and diseases which are recorded on the Medical History eCRF must include the toxicity grade when applicable.
- Disease history (MDS), including date of diagnosis, confirmation of MDS diagnosis, IPSS-R risk classification for MDS participants at time of screening, prior antineoplastic therapies. IPSS-R risk score for MDS participants should be calculated based on the hematology values obtained at screening.
- All prior and concomitant medications and medical procedures
- Blood transfusion **administered within 16 weeks** prior to enrollment

Other assessments will be completed to determine eligibility into the study as reported in [Table 8-1](#).

Assessments to be performed at screening include:

- Physical examination
- ECOG Performance Status, body height, weight, vital signs (blood pressure (supine position preferred when ECGs are collected) and pulse and body temperature).
- Laboratory - hematology, chemistry, coagulation, urinalysis, serum pregnancy test for women of child-bearing potential, thyroid function, [REDACTED] HIV serology (only if required per local regulation). If multiple laboratory tests were performed during screening to confirm eligibility, the lab values closest to enrollment should be used (last available values during screening).
- Cardiovascular assessments (i.e., triplicate 12-lead ECG)  
[REDACTED]
- Bone marrow biopsy or aspirate will be performed locally to establish diagnosis (If a bone marrow aspirate or biopsy was conducted during the regular work-up of the participant and falls within 28 days prior to enrollment; although prior to signing main study ICF it may be considered as the baseline assessment for the study).
- Cytogenetics will be performed locally as per local standard
- Patient reported outcomes  
[REDACTED]
- Adverse events

- Blood should be collected for phenotypic and molecular assessments

Subject race and ethnicity are collected and analyzed to identify variations in safety or efficacy due to these factors as well as to assess the diversity of the study population as required by Health Authorities.

Investigators will have the discretion to record abnormal test findings on the medical history CRF whenever in their judgment, the test abnormality occurred prior to the informed consent signature. Significant new findings that begin or worsen after informed consent must be recorded on the AE page of the subject's eCRF.

### 8.3 Efficacy

Efficacy assessments will be performed according to the IWG and WHO criteria for MDS ([Cheson et al 2000](#), [Cheson et al 2006](#), [Arber et al 2016](#), [Platzbecker et al 2018](#)). Response criteria in MDS are described in [Table 8-2](#). Investigators will assess locally at their site and document response/progression at each time point as per the visit schedule. For efficacy analyses, baseline is defined as the last non-missing assessment on or before the date of enrollment.

The hematological improvement per modified IWG-MDS criteria ([Cheson et al 2006](#)) will be assessed in all enrolled participants to report specific hematologic improvement (HI) of cytopenias in the three hematopoietic lineages: erythroid (HI-E), platelet (HI-P), and neutrophil (HI-N).

**Table 8-2 Modified response classification per IWG criteria in MDS**

([Platzbecker et al 2018](#), [Cheson et al 2006](#), [Cheson et al 2000](#))

Response category	Definition #
Complete remission (CR)	
Bone marrow:  <math>\leq 5\%</math> blasts with normal maturation of all cell lineages.            (Note: Persistence of dysplasia will be noted but does not preclude achievement of complete remission [CR])
 
Peripheral blood
 
 
1. Hgb <math>\geq 10</math> g/dL AND
 
2. Platelets <math>\geq 100*10^9/L</math> AND
 
3. Neutrophils <math>\geq 1.0*10^9/L</math> AND
 
4. Blasts 0%
 
 
Note: the participant must not receive RBC or platelet transfusions, myeloid growth factor within 2 weeks before this disease assessment

marrow Complete remission (mCR)	
Bone marrow:  <math>\leq 5\%</math> blasts and blast count decrease by <math>\geq 50\%</math> compared to baseline
 
Peripheral blood/transfusion:            Marrow CR may be achieved with or without improved blood counts or with or without transfusions

Partial remission (PR)	All CR criteria except Bone marrow: $\geq 50\%$ decrease from baseline in blasts in bone marrow AND blast count in bone marrow $>5\%$
Stable Disease (SD)	Failure to achieve at least PR, but no evidence of progression for $>8$ weeks
Relapse from CR	Only in participants with a CR: At least 1 of the following criteria is met: [In absence of another explanation not due to MDS, such as acute infection, bleeding, hemolysis, etc. Note that observation of peripheral blasts is not a sufficient criterion for relapse. However in that case, a bone marrow examination should be made to determine whether relapse has occurred.] 

1. Return to baseline bone marrow blast percentage

2. Decrease of <math>\geq 50\%</math> from maximum remission/response*** levels in neutrophils AND neutrophils <math><1.0*10^9/L</math>. Note: neutrophils counts during periods of active infection will not be considered in determining the maximum

3. Decrease of <math>\geq 50\%</math> from maximum remission/response*** levels in platelets AND platelets <math><100*10^9/L</math>

4. Decrease from maximum remission/response*** levels in Hgb concentration by <math>\geq 1.5\text{g/dL}</math> AND Hgb <math><10\text{ g/dL}</math>

5. Becoming transfusion dependent**

Disease progression	
At least 1 of the following criteria is met:
 
[In absence of another explanation not due to MDS, such as acute infection, bleeding, hemolysis, etc. Note that observation of peripheral blasts is not a sufficient criterion for progression. However in that case, a bone marrow examination should be made to determine whether relapse has occurred.]
 
Bone marrow according to the number of blasts of the participant at baseline:
 
 
1. Less than 5% blasts at baseline: <math>\geq 50\%</math> increase in blasts over baseline to <math>>5\%</math> blasts
 
2. 5%- <math><10\%</math> blasts at baseline: <math>\geq 50\%</math> increase over baseline to <math>>10\%</math> blasts
 
3. 10%- <math><20\%</math> blasts at baseline: <math>\geq 50\%</math> increase over baseline to <math>>20\%</math> blasts. Participants with more than 20% of blasts will be considered to have transformation to acute leukemia per 2016 WHO classification (Arber et al 2016)
 
 
Peripheral blood:
 
 
1. Decrease of <math>\geq 50\%</math> from maximum remission/response*** levels in neutrophils AND neutrophils <math><1.0 \times 10^9/L</math>. Note: neutrophils counts during periods of active infection will not be considered in determining the maximum
 
2. Decrease of <math>\geq 50\%</math> from maximum remission/response*** levels in platelets AND platelets <math><100 \times 10^9/L</math>
 
3. Reduction from maximum remission/response*** levels in Hgb by <math>\geq 2\text{g/dL}</math> AND Hgb <math><10\text{g/dL}</math>
 
 
Becoming transfusion dependent**
 
Occurrence of acute leukemia or extramedullary leukemia per investigator's judgement

----------------------------	---

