### 5.1 Inclusion criteria

Written informed consent must be signed by the patient prior to any screening procedures. Patients eligible for this study must meet **all** of the following criteria:

1. Signed informed consent must be obtained prior to participation in the study.
2. Age  $\geq 18$  years at the date of signing the informed consent form (ICF).
3. Morphologically confirmed diagnosis of a myelodysplastic syndrome (MDS) primary or secondary based on 2016 WHO classification (Arber et al 2016) by investigator assessment with one of the following Prognostic Risk Categories, based on the International Prognostic Scoring System (IPSS-R). Note: MDS diagnosis history will be recorded in the CRF:
  - Very high ( $> 6$  points)
  - High ( $> 4.5 - \leq 6$  points)
  - Intermediate ( $> 3 - \leq 4.5$  points)
4. Not suitable at time of screening for immediate myeloablative/ chemotherapy or hematopoietic stem-cell transplantation based on investigator assessment of age, comorbidities, local guidelines, institutional practice (any or all of these).
5. Eastern Cooperative Oncology Group (ECOG) performance status of 0, 1 or 2.
6. AST and ALT  $\leq 3 \times$  upper limit of normal (ULN).
7. Total bilirubin  $\leq 2 \times$  ULN (except in the setting of isolated Gilbert syndrome).
8. Estimated Glomerular Filtration Rate (eGFR)  $\geq 30$  mL/min/1.73m^2 (estimation based on Modification of Diet in Renal Disease (MDRD) formula, by local laboratory).
9. Patient is able to communicate with the investigator and has the ability to comply with the requirements of the study procedures.

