Response assessment will be performed by the investigator according to the assessment schedule depicted in protocol Table 8-1 based on available bone marrow assessment and peripheral blood every 3 cycles for core phase during the first 07 cycles and every 6 cycles for extension phase and all transfusions records as detailed in [Table 2-6](#) using the modified version of the published response criteria IWG for MDS. Moreover, response assessments can be performed at any time if clinically indicated, e.g. for confirmation of response but also for any suspicion of progression/relapse. These assessments are recorded as an unscheduled visit in the eCRFs and will be considered for the overall determination of response and progression/relapse with the respective assessment date.

The investigator does not determine best overall response, he/she is assessing only the response based on the given bone marrow and peripheral blood data, the history of transfusions and myeloid growth factor received within the last 2 weeks.

The best overall response (BOR) will be derived based on the CR secondary endpoint rules by Novartis as below:

- CR = at least one determination of CR without progression or relapse from CR within the four after CR.
- mCR = at least one determination of mCR (and not qualifying for a CR).
- PR = at least one determination of PR (and not qualifying for a CR/mCR).
- SD = at least one SD assessment and not qualifying for CR, mCR or PR.
- PD = progression after enrollment and not qualifying for CR, mCR, PR or SD.
- UNK = all other cases (i.e., not qualifying for confirmed CR or mCR or PR and without SD or progression).

Details on the definition of response categories which are to be captured in the eCRF by the investigator were defined in Table 8-2 of the protocol that was copied into Table 2-6 below.

Table 2-6 Modified response classification per IWG criteria in MDS

| Response category | Definition [#] |
|-------------------|-------------------------|
|-------------------|-------------------------|

| | |
|--|--|

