| Complete remission (CR) | 
Bone marrow: $\leq 5\%$ blasts with normal maturation of all cell lineages. (Note: Persistence of dysplasia will be noted but does not preclude achievement of complete remission [CR])
 
Peripheral blood
 
 1. Hgb ≥ 10 g/dL AND 2. Platelets $\geq 100*10^9/L$ AND 3. Neutrophils $\geq 1.0*10^9/L$ AND 4. Blasts 0% 
Note: the subject must not receive RBC or platelet transfusions, myeloid growth factor within 2 weeks before this disease assessment
 |
| marrow Complete remission (mCR) | 
Bone marrow: $\leq 5\%$ blasts and blast count decrease by $\geq 50\%$ compared to baseline
 
Peripheral blood/transfusion: Marrow CR may be achieved with or without improved blood counts or with or without transfusions
 |
| Partial remission (PR) | 
All CR criteria except
 
Bone marrow: $\geq 50\%$ decrease from baseline in blasts in bone marrow AND blast count in bone marrow $>5\%$
 |
| Stable Disease (SD) | Failure to achieve at least PR, but no evidence of progression for >8 weeks |
| Relapse from CR | 
Only in subjects with a CR:
 
At least 1 of the following criteria is met:
 
[In absence of another explanation not due to MDS, such as acute infection, bleeding, hemolysis, etc. Note that observation of peripheral blasts is not a sufficient criterion for relapse. However in that case, a bone marrow examination should be made to determine whether relapse has occurred.]
 
 • Return to baseline bone marrow blast percentage • Decrease of $\geq 50\%$ from maximum remission/response*** levels in neutrophils AND neutrophils $<1.0*10^9/L$. Note: neutrophils counts during periods of active infection will not be considered in determining the maximum • Decrease of $\geq 50\%$ from maximum remission/response*** levels in platelets AND platelets $<100*10^9/L$ • Decrease from maximum remission/response*** levels in Hgb concentration by ≥ 1.5 g/dL AND Hgb <10 g/dL • Becoming transfusion dependent** |

| | |
|----------------------------|---|

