| Disease progression | 
At least 1 of the following criteria is met:
 
[In absence of another explanation not due to MDS, such as acute infection, bleeding, hemolysis, etc. Note that observation of peripheral blasts is not a sufficient criterion for progression. However in that case, a bone marrow examination should be made to determine whether relapse has occurred.]
 
Bone marrow according to the number of blasts of the subject at baseline:
 
 1. Less than 5% blasts at baseline: $\geq 50\%$ increase in blasts over baseline to $>5\%$ blasts 2. 5%- $<10\%$ blasts at baseline: $\geq 50\%$ increase over baseline to $>10\%$ blasts 3. 10%- $<20\%$ blasts at baseline: $\geq 50\%$ increase over baseline to $>20\%$ blasts. Subjects with more than 20% of blasts will be considered to have transformation to acute leukemia per 2016 WHO classification (Arber et al 2016) 
Peripheral blood:
 
 1. Decrease of $\geq 50\%$ from maximum remission/response*** levels in neutrophils AND neutrophils $<1.0 \times 10^9/L$. Note: neutrophils counts during periods of active infection will not be considered in determining the maximum 2. Decrease of $\geq 50\%$ from maximum remission/response*** levels in platelets AND platelets $<100 \times 10^9/L$ 3. Reduction from maximum remission/response*** levels in Hgb by $\geq 2\text{g/dL}$ AND Hgb $<10\text{g/dL}$ 
Becoming transfusion dependent** Occurrence of acute leukemia or extramedullary leukemia per investigator's judgement
 |
|----------------------------|---|

| Modified Hematological Improvement per IWG-MDS criteria in MDS (Cheson et al 2006) | |
|---|---|
| HI category | Definition[#] (HI must last at least 8 weeks) |
| Erythroid response (HI-E) (pretreatment*, $<11\text{ g/dL}$) | 
 1. Hgb increase from baseline by $\geq 1.5\text{ g/dL}$, in at least 2 consecutive Hgb measurements and maintained over at least 8 weeks 2. Relevant reduction from baseline of units of RBC transfusions by an absolute number of at least 4 RBC transfusions/8 weeks compared with the pre-treatment transfusion number in the previous 8 weeks. Only RBC transfusions given for a Hgb of $<9\text{ g/dL}$ pre-treatment will count in the RBC transfusion response evaluation. |

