2.7.1.5 Response Rates

Response rate is defined as the proportion of subjects with best overall response of either complete remission (CR)/marrow remission (mCR)/partial remission as per investigator assessment according IWG- MDS at any time during the study (on or before cut-off date) ([Table 2-6](#)). The number and percentage of subjects with all other responses rates will be summarized.

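### Marrow CR has no minimum baseline blast count and needs one determination, so low-blast entrants can enter the CR/mCR/PR response rate through counting noise

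*Protocol*

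**What the plan says.** Protocol 8.3 (Table 8-2) and SAP Table 2-6 give the same two marrow conditions for mCR: at most 5% "blasts and blast count decrease by" at least 50% against baseline. Neither table says how many blasts must be present at the start. On the blood side, "Marrow CR may be achieved with or without improved blood counts or with or without transfusions".

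The best-overall-response rule in SAP 2.7.1.1 reads "mCR = at least one determination of mCR (and not qualifying for a CR". The line for CR adds a condition: "CR = at least one determination of CR without progression or relapse from CR within the four after CR" (the time unit is missing in the text). The mCR line adds none. SAP 2.7.1.5 then puts mCR into the rate: "Response rate is defined as the proportion of subjects with best overall response of either complete remission (CR)/marrow remission (mCR)/partial remission".

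On entry, Protocol 5.1 asks for "Morphologically confirmed diagnosis of a myelodysplastic syndrome (MDS) primary or secondary based on 2016 WHO classification" with an IPSS-R score above 3, and no minimum marrow blast percentage. Protocol 1.1 describes IPSS-R as built from blasts, cytopenias and cytogenetics, so blasts need not be raised. The progression rule in both tables has its own stratum, "Less than 5% blasts at baseline", so such participants are expected.

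The efficacy baseline is one value, the last non-missing assessment up to enrollment (Protocol 8.3). Response is judged locally and central review is optional. SAP section 4 says that no supportive, subgroup or sensitivity analysis is performed.

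**The concern.** For a participant with at most 5% marrow blasts at entry, the first mCR condition holds before any treatment. The second is relative, and at low percentages a halving is a matter of a few cells. One such reading among several marrows, with no change in blood counts, sets best overall response to mCR. Within this subgroup the rule can only add responders.

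The same tables handle hematologic improvement differently. Each lineage response is open only to participants whose pretreatment value was abnormal (hemoglobin below 11 g/dL, platelets below 100 x 10^9/L, neutrophils below 1.0 x 10^9/L). mCR has no equivalent gate.

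At stake is what the CR/mCR/PR percentage (secondary endpoint 5) can be taken to show. It may credit participants who had no excess blasts to clear, and no planned summary separates them.

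**Working it through.** The documents state no figure for mCR noise, so there is no planned number to reproduce. The check asks how often the rule is met when nothing changes.

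**Inputs from the documents**
- The rule: at most 5% blasts, a fall of at least 50%, one determination (Table 8-2, Table 2-6, SAP 2.7.1.1).
- Number of looks. Protocol 8.3 schedules on-treatment marrows at C4D1, C7D1, C10D1 and C13D1. The response assessment row of Table 8-1 shows only cycle 7, cycle 13, end of treatment and when clinically indicated. SAP 2.7.1.2 says response is assessed at least at each marrow, every 3 cycles. Both two and four looks are therefore shown.
- Denominator: 39 enrolled (SAP 1.1), all assumed dosed.

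**Assumptions not in the documents**
- 200 or 500 cells counted per marrow.
- True blasts constant at 2% or 3%.
- Independent binomial counting error and nothing else.
- The rule applied mechanically.

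**Formula.** The baseline count is B ~ Binomial(N, p), with 1 <= B <= 0.05N. Each later count is X ~ Binomial(N, p). Given B = b, one look meets the rule with probability q(b) = P(X <= floor(b/2)). The 5% ceiling is then met automatically. With k looks,

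P(false mCR) = sum over b of P(B = b)[1 - (1 - q(b))^k] / sum over b of P(B = b).

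**One term worked.** N = 500, p = 2%, b = 10: q = P(X <= 5) = 0.0652. Two looks give 1 - 0.9348^2 = 0.126; four looks give 1 - 0.9348^4 = 0.236. Averaging over b gives the table.

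| Cells | True blasts | 1 look | 2 looks | 4 looks |
|---|---|---|---|---|
| 500 | 2% | 8.2% | 14.9% | 25.4% |
| 500 | 3% | 3.8% | 7.1% | 13.0% |
| 200 | 2% | 22.1% | 36.8% | 54.9% |
| 200 | 3% | 13.7% | 24.3% | 39.6% |

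The result is sensitive to true blasts. At four looks it is 48% (true 1%) and 4% (true 4%) with 500 cells, and 76% and 23% with 200 cells.

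**Effect on the rate.** Points added = 100 x m x P / 39, where m is the number of participants entering at 2-3%. The documents do not give m.
- m = 4: from 100 x 4 x 0.0714 / 39 = 0.7 to 100 x 4 x 0.549 / 39 = 5.6 points.
- m = 10: from 1.8 to 14.1 points.
- m = 16: from 2.9 to 22.5 points.

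In each line the low end is 500 cells, true 3%, two looks; the high end is 200 cells, true 2%, four looks. For scale, Protocol 4.3.2 reports earlier mCR shares of 3/18 = 16.7% and 7/19 = 36.8%.

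**With mCR restricted to baseline blasts above 5%.** False mCR among participants observed at 5% or below is zero by construction. Noise just above the cut remains: with true blasts of 6% and four looks, 17.5% at 200 cells and 1.9% at 500 cells.

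**The case against.** **Reach.** mCR enters one secondary endpoint among eight. CR and mCR are separate categories, CR has its own rate with an exact interval, and nothing is tested. This stands and bounds the point.

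**Size.** Cell counts and the baseline blast distribution are assumed. Two looks rather than four give clearly smaller figures. Early discontinuation lowers them further. A participant who also reaches CR is a responder anyway, and some falls at low blast counts are real. The investigator records the category and may not apply the 50% rule mechanically. All of this stands, so the figures describe the rule's exposure to noise and do not estimate bias in this trial.

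**Transparency.** SAP 2.7.1 already plans to list best overall response and marrow blast percentages. A careful reader could find every mCR that began at or below 5%. That helps, but a listing leaves the summarized rate unchanged.

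**Stronger readings that the documents do not support**
- A reader might infer that the inflation favors the drug against historic hypomethylating-agent data. Protocol 4.5 makes that comparison for an earlier study, as background. None is planned here, and nothing shows that the historic series used a different mCR rule.
- A reader might infer that CR has the same flaw, because a participant could meet it unchanged from baseline. CR also requires normal maturation of all lineages, no peripheral blasts, hemoglobin, platelet and neutrophil minimums, and no transfusion or growth factor in the preceding two weeks. The documents give no sign that entrants with IPSS-R above 3 would commonly meet all of these.

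**Conclusion.** The point holds for the CR/mCR/PR response rate only. As written, the rule can count a participant who entered with at most 5% marrow blasts as a responder on one reading, without any real change, and no planned analysis shows how many responders arise this way.

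Under unchanged true blasts of 2-3% and counting error only, the chance per low-blast participant is about 7-15% (two looks) to 13-25% (four looks) with 500-cell counts, and 24-37% to 40-55% with 200-cell counts. The effect on the reported rate cannot be fixed without the number of low-blast entrants and the cell counts. Net inflation is smaller where the participant also reaches CR, leaves early or has a genuine fall.

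This justifies an added line in the report. It does not justify replacing the main definition, because the current SAP addendum is dated after database lock and a new main definition at that stage would be post hoc.

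**What to change.** In SAP 2.7.1.5, keep the protocol definition as the pre-specified line. Beside it, report:
- mCR split by baseline marrow blasts, 5% or below versus above 5%;
- the CR/mCR/PR rate with mCR counted only when baseline blasts are above 5%, labelled as added after database lock;
- the baseline blast percentage for each participant with mCR.

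Also state how a 0% baseline is handled, since a 50% fall from zero is undefined.

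The cost is one derived baseline flag, using marrow data already collected and due to be listed. The added rate may be slightly lower, and it scores genuine falls in low-blast participants as non-response, which is why it sits beside the protocol line. It does not remove noise in participants just above 5%.
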